8.6 REMINDERS

Over the first 12 weeks of the study, participants will receive an email or text reminder to engage with their assigned program every other week (for a total of 6 reminders). These reminders will be sent out during weeks 1, 3, 5, 7, 9 and 11. Two of these communications will remind participants of the availability of NRT. During the first week of the study, participants may receive up to an additional two text or email messages reminding them to log into their study app and confirm they have done so.

Participants will receive periodic reminders from study staff to complete their questionnaires via email, text or phone, as needed. All participants will receive all questionnaires, regardless of completion of previous questionnaires. [REDACTED]
[REDACTED]
[REDACTED]

8.7 STUDY COMPLETION

The final study questionnaire will be emailed at 104 weeks (2 years) after enrollment. Completion of this questionnaire, or 110 weeks after enrollment (whichever comes first) will signify study completion. For participants who report 7-day (or greater) abstinence at 104 weeks and agree to participate in a biovalidation visit, completion of this visit, or 110 weeks after enrollment (whichever comes first) will signify study completion.

8.8 SCHEDULE OF STUDY ACTIVITIES

[REDACTED]

9. DATA COLLECTION

Study personnel will collect information from the participant over the course of the study including:

- Age
- Gender
- Pregnancy status (self-reported) in women
- Race/ethnicity
- Employment status
- Education
- Type of smartphone participant uses (iPhone or Android)
- Number of years smoking
- Social and living environment relating to smoking
 - Live with other adults who smoke
 - Live with romantic partner who smokes
 - Number of close friends who smoke
- Alcohol use (AUDIT-C, 3 items)
- Screening for depressive symptoms (CES-D, 10 items)
- Quit attempts
 - Past 12 months
 - During the study
- Number of cigarettes currently smoked per day (CPD)
- 7-day point prevalence abstinence (PPA) (self-reported and biovalidated)
- 30-day point prevalence abstinence (PPA) (self-reported and biovalidated)
- Abstinence from all tobacco products (self-reported)
- Continuous abstinence (self-reported and biovalidated)
- Use of other tobacco products other than cigarettes including pipes, cigars, cigarillos, little filtered cigarettes, hookah, water pipe, any electronic cigarette product (e-cigs, vape, vapor), smokeless tobacco, chew, or snuff, and any other inhaled combustible material
- Use of smoking cessation medications past and present
- Use of other smoking cessation methods, past and present (for the present, methods other than those in the study program)
- Attitudes towards smoking
 - Desire to quit (y/n)
 - Confidence to quit (scale 1-10)
 - Perceived difficulty of staying quit (scale 1-10)
 - Self-efficacy
- Engagement
 - App opens (self-reported)
 - Number of days with app opens (self-reported)
 - Number of weeks with app opens (self-reported)
- Feedback on assigned program set-up and use
 - Ease/difficulty getting started
 - Use experience

- Design
- Impact on quitting
- Impact on staying quit
- How would you improve the experience of your assigned program?
- How likely are you to recommend your assigned program to a friend/colleague? (scale 1-10)
- How has using your assigned program affected the number of cigarettes you smoke per day? (increase, no change, decrease)
- Which of the following best describes your thoughts on your assigned program? ('nothing else can help me with smoking' to 'it will not help me with smoking')
- Which of the following best describes your assigned program's ability to help someone quit smoking? ('extremely helpful' to 'makes quitting smoking harder')
- Which of the following best describes what you have learned from using your assigned program ('really unique/key insights' to 'I am more confused after using the program')
- Which of the following best describes your need for your assigned program? ('I really need this program' to 'I am not interested at all in this program')
- What has been the most helpful part of your program?
- What has been the most frustrating part of your program?
- My study program helped me quit smoking – True or False
- Skills I learned in my study program have helped me stay quit – True or False
- My study program helped me with my goals related to smoking– True or False
- NRT
 - Have you ordered nicotine replacement therapy (patches, gum and/or lozenges)? Why or Why not?
 - Over the last 7 days, how many days have you used nicotine replacement therapy (nicotine patches, gum and/or lozenges)?
 - Over the last 7 days, which types of nicotine replacement therapy have you used?
 - For about how many weeks have you used NRT since the study started?
 - Since you began the study, have you purchased or obtained nicotine replacement therapy (patches, gum and/or lozenges) outside of what was provided by the study?

10. TECHNICAL APPROACH AND STUDY DESIGN

10.1 ACCEPTANCE CRITERIA

Data will be accepted if the participant meets eligibility criteria, and completes the electronic informed consent form, the Baseline Questionnaire and reports a date they first opened their assigned study app.

10.2 ADVERSE EVENTS

Participants will be asked to detail any issues with their assigned smoking cessation program and/or NRT on the 26- and 52-week questionnaires. In addition, participants may offer up such issues at any point during the study by reaching out to study staff and/or customer service. The study sponsor follows a department operating procedure (DOP-1748, Clinical Adverse Event Reporting, [REDACTED]) for adverse event

reporting. In accordance with the sponsor's adverse event policy, Quality Assurance will be made aware of these issues. Additional information will be sought from participants reporting issues, as needed. Upon collection of adequate information on the issue, or an adequate good-faith effort to obtain such information, a determination will be made regarding any associated reporting requirements, in compliance with DOP-1748 and Quality Assurance reporting policies.

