Finally, participants will have the option to select, order and use over-the-counter nicotine replacement therapy (NRT). Participants are provided with on-label information about the NRT, and are required to acknowledge their standing relating to contraindications for NRT use before being able to order the NRT. They then select, order and use the NRT as they would when purchasing over-the-counter medications in everyday life. The NRT is provided free of charge to study participants who order it. Risks associated with NRT use are identified in the labeling provided to study participants [REDACTED].

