2.3.3 Risk Benefit Assessment

Given the non-invasive nature of Pivot and QuitGuide and study data collection, there are minimal anticipated risks. These risks relate to breach of confidentiality in the circumstance of a data breach, possible participant anxiety related to using the Pivot Breath Sensor or related to performing biovalidation with the sensor during videocalls, and possible side effects of the use of over-the-counter NRT if the participant chooses to use it. These risks have been mitigated to the extent possible through data protection measures, through enabling participants to ultimately decide if and when to do breath samples, through fully informing participants why the biovalidation is being done, what it tests for and asking if they would like to proceed with the testing on the applicable videocalls, and through enabling participants to make an informed decision on if they will use NRT and which NRT they will use if they choose to use any at all. Breath samples, biovalidation, NRT selection and NRT use are at the participant's discretion and are not mandated. Indeed, no specific use of Pivot or QuitGuide overall is required. Participants will have the remote support of study staff and customer support as they need over the course of the study. Participants are not required to change their smoking behavior. No medical decisions are made based on study data.

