- Number of quit attempts at 4, 12, 26, 52, and 104 weeks (defined as answering ≥ 1 to the following question: “Since you began the study, how many times have you tried to quit smoking where you've gone at least 1 day without smoking a cigarette, even a single puff?”).
- User satisfaction with the smoking cessation program (set-up and getting started with program, recommend to friend, program design, program was useful for quitting, program helped me quit, program helped me stay quit) at 2, 3, 4, 5, 12, 26, 52 and 104 weeks
- Engagement with program, collected weekly during the first 12 weeks after enrollment:
 - Number of times app opened (self-report)
 - Number of days in which app was opened (self-report)
 - Number of weeks in which app was opened (self-report)
- Participant changes in self-efficacy at 6, 12, 26 and 52 weeks
- Participant changes in self-reported health and wellbeing at 26 and 104 weeks
- Self-reported NRT use at 4, 8, 12, 26, 52 and 104 weeks
- Use of other smoking cessation tools (apps, counseling, non-study medications, etc.) at 12, 26, 52, and 104 weeks
- Alcohol use behavior at 12, 26 and 52 weeks (Alcohol Use Disorders Identification Test-Concise or AUDIT-C screening questionnaire, 3 items) [18-20]
- Presence of depressive symptoms screening at 12, 26, and 52 weeks (Center for Epidemiological Studies Depression Scale or CES-D screening questionnaire, 10 items) [11,21-23]
- Living and social environment relating to cigarette smoking at 12, 26 and 52 weeks (live with other adults who smoke, live with romantic partner who smokes, number of close friends who smoke)
- Adverse events at 26, 52 weeks

Eligibility Criteria

The study population comprises current smokers, 21 years of age and above, who own and

regularly use a smartphone and are ready to quit smoking in the next 30 days.

Inclusion Criteria

- 21+ years of age
- Current daily cigarette smokers (at least 5 cigarettes per day) for the past 12 months
- Plans to quit smoking in the next 30 days
- Resident of the United States
- Able to read and comprehend English
- Owns and uses a smartphone compatible with the study app (iPhone 5 and above with operating system iOS 12 and above, or, Android 7.0 and above with operating system Android 7.0 and above)
- Has daily internet access on smartphone
- Comfortable downloading and using smartphone apps
- Willing to sign the Informed Consent Form

Exclusion Criteria

- Pregnancy (self-reported)

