8.3 ACTIVE PROGRAM USE

The participant will initiate use of their assigned program. To be considered enrolled, one must: sign the electronic informed consent form, complete the Baseline Questionnaire, and provide the date they first logged in to their assigned app. Participants may receive up to two text or email messages during the first week of the study reminding them to go into their study app and confirm they have done so. There is no pre-determined time limit on how long a participant can actively engage in their app, although it is expected most participants will complete engagement by 6 months from enrollment. For individuals enrolled in the intervention arm, coaching is available for up to 12 months from enrollment. In both arms, participants may order up to 12 weeks of NRT, in two-week increments over the first 12 months of the study. Pivot is designed to be a 12-month program. There is one possible biovalidation videocall visit at 12 weeks during this portion of the study and weekly online questionnaires at the end of weeks 1 through 12.

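### Adverse events, a listed secondary outcome, have stated solicited questions only at weeks 26 and 52, so an event in weeks 0-12 is first asked about 14 to 26 weeks later, and no question is stated after week 52.

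*Combined protocol and SAP*

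**What the plan says.** The synopsis and section 7.3 both list adverse events among the secondary outcomes. Section 7.3 sets the timing as "Adverse events at 26, 52 weeks". Section 10.2 agrees: "Participants will be asked to detail any issues with their assigned smoking cessation program and/or NRT on the 26- and 52-week questionnaires". The question it describes covers issues with the assigned program and/or NRT.

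The same section keeps a spontaneous route open, since "participants may offer up such issues at any point during the study". Reports go to Quality Assurance, and more information is sought as needed. Section 2.3.3 adds that "Participants will have the remote support of study staff and customer support as they need over the course of the study".

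The questionnaire schedule is denser than the adverse-event schedule. Section 8.3 provides for "weekly online questionnaires at the end of weeks 1 through 12", and section 8.4 adds questionnaires at weeks 26, 52 and 104. Exposure to NRT is tracked early: "Self-reported NRT use at 4, 8, 12, 26, 52 and 104 weeks" (section 7.3).

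Contact with the program differs by arm. Section 6.6 describes coach outreach about once a week for Pivot users. Section 7.9 puts a customer-support number in the breath sensor labeling provided to the intervention arm, whereas technical help for QuitGuide comes from QuitGuide itself.

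**The concern.** The risks named in sections 2.3.1 and 2.3.3 include NRT side effects and anxiety from using the breath sensor. Exposure to both can begin soon after randomization: the app is available at once, NRT can be ordered in two-week increments during the first 12 months, and two of the six reminders in weeks 1-11 mention NRT. In that period the plan asks three times whether NRT was used. On the stated timing, it does not ask whether it caused a problem until week 26. A minor early event that the participant does not volunteer may be forgotten by then. Someone who answers the early questionnaires but neither the week 26 nor the week 52 one is never asked.

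Before week 26 the outcome therefore rests on participants' own initiative, and the two arms do not have the same occasions to speak up. After week 52 the same is true for the rest of the study, although a week 104 questionnaire is sent. At stake is how complete one secondary outcome is, and how plainly a table by arm can be read.

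**Working it through.** **Check on the schedule.** Section 7.6 states 16 compensated questionnaires. One at baseline (7.5), 12 weekly (8.3) and three in follow-up (8.4) give 1 + 12 + 3 = 16. The count reproduces, so the early questionnaires that could carry the question exist.

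**Inputs.** Stated adverse-event questions: weeks 26 and 52 (7.3, 10.2). Questionnaires available: weeks 1-12, 26, 52 and 104. NRT-use items: weeks 4, 8, 12, 26, 52 and 104 (7.3).

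**Formula.** Lag = week of the first solicited question at or after the event, minus the week of the event. The means assume events spread evenly within each window. The documents give no event distribution, so that is an assumption. The ranges do not depend on it.

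**Weeks 0-12, as written.** Event at week 0: 26 - 0 = 26 weeks. Event at week 12: 26 - 12 = 14 weeks. Mean: 26 - 6 = 20 weeks.

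**Lag in weeks by window:**

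| Event window | As written | Items added at 4, 8, 12 and 104 |
|---|---|---|
| 0-12 | 14 to 26, mean 20 | at most 4, mean 2 |
| 12-26 | at most 14, mean 7 | unchanged |
| 26-52 | at most 26, mean 13 | unchanged |
| 52-104 | no question stated | at most 52, mean 26 |

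**Mean over weeks 0-26:**

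- As written: (12 × 20 + 14 × 7) / 26 = 338 / 26 = 13.0
- Week 12 item only: (12 × 6 + 14 × 7) / 26 = 170 / 26 = 6.5
- Items at weeks 4, 8 and 12: (12 × 2 + 14 × 7) / 26 = 122 / 26 = 4.7
- Items in all 12 weekly questionnaires: (12 × 0.5 + 14 × 7) / 26 = 104 / 26 = 4.0

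Three items capture nearly all of the gain that twelve would give, and they fall on questionnaires that already ask about NRT use.

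**Limits.** These figures are elapsed time, and they assume that the questionnaires are answered. The documents give neither an event rate nor a rate of recall loss, so lag cannot be turned into a count of missed events.

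**The case against.** The strongest reply is that the schedule is a deliberate choice and breaks no rule in the plan. Sections 7.3 and 10.2 agree. Section 10.3 calls the interventions standard and low-risk. Listed contraindications are excluded at entry, and participants "are required to acknowledge their standing relating to contraindications for NRT use before being able to order the NRT" (section 2.3.1). NRT can be ordered over 12 months, so weeks 26 and 52 cover that period at two even points, and nothing shows that events cluster early. All of this stands, and it is why the point is minor. It does not make the outcome as complete as the existing questionnaires would allow.

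Second, other items may surface problems: satisfaction questions at weeks 2, 3, 4, 5 and 12, and the open question "What has been the most frustrating part of your program" (section 9). They may, but they are not described as adverse-event items. The schedule of activities in section 8.8 is redacted and the questionnaire forms are not shown, so an unlisted early item cannot be excluded. The point rests on the timing stated in the readable text.

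Third, the change may come too late. Rev 7 added a 104-week visit, which suggests, without proving, that many or all participants are past week 12. This stands. It limits the early items to whoever can still receive them. It also means that a mid-study change would mix two solicitation schedules, which the tables must keep apart.

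A reader might go further and infer that early safety is unmonitored, or that adverse-event counts are biased between arms. The documents support neither. Spontaneous reporting is open to everyone throughout. The different contact routes make unequal reporting possible but do not show that it occurs or in which direction.

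**Conclusion.** The point holds as a minor one. On the stated timing, an event in weeks 0-12 waits 14 to 26 weeks for the first solicited question, and an event after week 52 has none. The ranges follow directly from sections 7.3 and 10.2; the mean of 20 weeks needs the even-spread assumption.

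The effect is confined to the completeness of one secondary outcome. App opens, the primary outcome, are untouched, and section 11.2 specifies no adverse-event comparison between arms, so no planned test is shown to change. The conclusion assumes that the redacted schedule and forms contain no further solicited adverse-event item. This is an inexpensive improvement to a consistent plan, and the sections do not contradict each other.

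**What to change.** 1. For participants who have not yet passed those weeks, put the question used at weeks 26 and 52 on the week 4, 8, 12 and 104 questionnaires in both arms. Amend sections 7.3 and 10.2 to list weeks 4, 8, 12, 26, 52 and 104.
2. Tabulate reports by arm, with solicited and spontaneous reports apart. Within solicited reports, separate participants asked under the present two-point schedule from those asked under the amended one.
3. For participants already past week 12, state in the study report (section 11.3) that the protocol scheduled no solicited adverse-event question before week 26, so early events rest on recall at week 26 or on spontaneous report. Word it as what the protocol scheduled, since the forms cannot be checked here.

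The cost is one question on four existing questionnaires, an IRB amendment, slightly longer forms and more minor reports to process. Revs 4, 5 and 7 already added questionnaire items during the study, so the change is of a familiar kind. If every participant is past week 12, the early items fall away. The week 104 item still applies to anyone who has not reached that week, and the tabulation and the report statement need no new data.

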- Health contraindications to nicotine patch use (irregular heartbeat, high blood pressure not controlled with medication, heart attack or stroke within the last 2 months, pregnant or breast feeding, skin allergies to adhesive tape or serious skin problems, stomach ulcers, history of seizures)
- Using other smoking cessation support, including apps and/or actively taking medication to quit smoking
- Daily marijuana use
- Residence with another person who is a participant in this study
- Immediate family member is a participant in this study
- Failure to provide contact or collateral information, failure to verify email address, and/or failure to demonstrate videoconference capability
- Participation in a previous study sponsored by Pivot Health Technologies Inc. (formerly Carrot Inc.)

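### Section 10.2 elicits adverse events as issues with the program or NRT, so health events a participant does not link to either are not systematically collected

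*Combined protocol and SAP*

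**What the plan says.** The synopsis lists adverse events among the secondary outcomes, and section 7.3 gives the time points: "Adverse events at 26, 52 weeks".

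Collection is described only in section 10.2. The solicited route is this: "Participants will be asked to detail any issues with their assigned smoking cessation" program or NRT, with the item placed on the week-26 and week-52 questionnaires. The unprompted route follows: "participants may offer up such issues at any point during the study by reaching out to study staff and/or customer service".

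On handling, section 10.2 says that "Quality Assurance will be made aware of these issues", that more information is sought where needed, and that "a determination will be made regarding any associated reporting requirements", in line with DOP-1748 (the sponsor's adverse event reporting procedure, redacted) and Quality Assurance policy.

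Section 7.3 also lists other health-related measures as outcomes in their own right, for example: "Participant changes in self-reported health and wellbeing at 26 and 104 weeks". The CES-D depression screen and AUDIT-C are collected at weeks 12, 26 and 52.

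**The concern.** An adverse event is ordinarily recorded first and judged for relatedness second. As section 10.2 describes the item, the order is reversed: the participant has to see something as a problem with the program or NRT before the item asks for it. That judgement is made by lay participants who know their arm, and in a trial where NRT is chosen and used at their own discretion.

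Two things are at stake. First, the sponsor cannot assess relatedness for an event it never receives, and no later analysis can restore it. The counts would then reflect what participants attributed to a product and could not be read as the incidence of health events by arm. Second, a question about problems with a program naturally draws technical and usability complaints, which are not health events. If these are not sorted out, they blur the same outcome.

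**Working it through.** No formula applies. The check sets the relevant sections side by side and asks what route each kind of report has into the outcome.

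1. **How often the item is asked.** Section 7.6 gives 16 questionnaires. That matches one at baseline (7.5), twelve weekly (8.3) and three at weeks 26, 52 and 104 (8.4): 1 + 12 + 3 = 16. Section 10.2 names 2 of the 16. Weeks 1 to 12 and week 104 are not named, so from week 52 to week 104 only the unprompted route is described.

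2. **What the two routes cover.** Both are defined by reference to the program or NRT; the unprompted route refers back to the same kind of issue.

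| Report | Within the solicited item as described? | Within the unprompted route as described? |
|---|---|---|
| Health event the participant links to the program or NRT | Yes | Yes |
| Health event the participant does not link to either | No | No, though nothing stops the participant from mentioning it |
| Technical or usability problem with the program | Yes | Yes |

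3. **Whether another source fills the second row.** Section 4 does not define an adverse event. The list in section 9 has no open question on new symptoms, illness or hospital care. That list is introduced as a set of inclusions and also omits the health and wellbeing measure named in 7.3, so its silence is evidence but not proof. CES-D, AUDIT-C and health and wellbeing may show some change in health, but no section links them to adverse event recording. Section 11.2 names no analysis specific to adverse events, and section 10.3 states that there is no data safety monitoring board.

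4. **Whether a later step fixes the third row.** The visible step decides on reporting requirements. No visible text sorts a report into health event or product complaint. DOP-1748 may do so. Section 9 also collects program problems separately as feedback, such as the most frustrating part of the program, but section 10.2 does not say how the two are kept apart.

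5. **Whether a later step fixes the second row.** DOP-1748 is cited for handling issues that have already been raised. As described, it does not reach events that nobody was asked about.

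**The case against.** The strongest reply is that the instrument itself is not visible. Section 10.2 summarises the week-26 and week-52 items in one sentence. The items, the schedule in section 8.8 and DOP-1748 are not in the public text. The real prompt may be broader than the summary, and the procedure may separate complaints from adverse events. This stands in part: it limits the usability half to something that may happen, and it means the first half concerns collection as the protocol describes it. It does not remove the point, because the protocol's own description is product-linked and nothing visible contradicts it.

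A second reply is proportionality. Sections 2.3.3 and 10.3 argue that the apps and over-the-counter NRT are low-risk. The trial is a pilot powered on app opens (7.7), and no visible between-arm safety claim rests on this outcome. That is fair and keeps the priority moderate. Even so, the plan lists the outcome, and improving it costs little.

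A reader might go further in three ways that the documents do not support:

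- **That unattributed events are lost.** Participants may contact staff at any time, and CES-D and the wellbeing measure may pick up some changes. The supportable statement is that such events are not systematically elicited as adverse events.
- **That the exclusion list shows which NRT harms would be missed.** It names conditions such as "irregular heartbeat, high blood pressure not controlled with medication, heart attack or stroke within the last 2 months", but as contraindications at entry. A contraindication is not a list of expected harms, and the NRT labeling that states the risks is redacted.
- **That complaints will inflate the Pivot count by a calculable amount.** Pivot has more components, but the documents give no complaint rates. Control participants who report abstinence may also be sent a breath sensor (8.5), and complaints may be sorted downstream.

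**Conclusion.** The concern holds in a limited form. As section 10.2 describes it, adverse event collection depends on the participant linking an event to the program or NRT, in an open-label trial. Health events outside that link have no systematic route into the section 7.3 outcome. Program and usability complaints may be mixed in unless DOP-1748 separates them.

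The number of events affected cannot be estimated, because the documents give neither an expected event rate nor an attribution rate. The structural size is clear: both of the two solicited occasions, in both arms, are product-linked.

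The conclusion assumes that the unseen questionnaire items match section 10.2's description and that no unseen item asks a neutral health question. If one does, the remedy is a sentence in section 10.2 saying so. The primary outcome is unaffected. This is a worthwhile, inexpensive improvement to a secondary outcome.

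**What to change.** 1. On the week-26 and week-52 questionnaires, ask both arms the same attribution-neutral question about any new or worsened health problem. The reference period should be since the study began at week 26, and since the week-26 questionnaire at week 52.
2. Ask about technical or usability problems in a separate item, and keep those answers out of the adverse event count.
3. In section 7.3, define the adverse event outcome as the answers to the health question plus spontaneous reports of health events.
4. State in section 10.2 that relatedness to the program or NRT is assigned afterwards under DOP-1748, and does not decide whether an event is recorded.

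The cost is splitting an item on two existing questionnaires. Section 15 shows that questions have been added to the week-12, 26, 52 and 104 questionnaires before. The downside is more unrelated minor events to log and classify in up to 180 people. Recall also remains long, at 26 weeks for each of the two periods (0 to 26 and 26 to 52), so brief or mild events will still be under-reported. The change adds no solicited question after week 52.
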